SA1. Quantify the extent that SDB and its subtypes are associated with PAF. This aim will be addressed by fitting conditional logistic regression models that condition on the matched pair. We will separately analyze each SDB variable (primary variable: AHI) to obtain an estimate and 95% CI of the odds ratio of PAF for a 1-unit increase in the SDB exposure. Non-linear effects between SDB and the log odds of PAF will be assessed using restricted cubic splines. Knots for the spline will be based on the SDB threshold at which PAF risk increases. Unadjusted and hierarchical adjusted models will be performed using the covariates listed above.

The secondary exposure variables (e.g. hypoxia, OAHI, CAI, AI) will be considered in separate models.

Exploratory Aim 1a. Cardiac structure, autonomic and biochemical variables (Table 2) will explain a proportion of the SDB and PAF relationship. This aim will be addressed by applying Pearl's mediation formula¹⁰⁸ to the conditional logistical regression model. This approach will allow a causally sound definition of the mediation effect of a given intermediate variable in the relationship between SDB (defined by AHI) and PAF. The approach involves a model for each mediator (e.g. a general linear model for a continuous mediator) and possibly a random effect to account for clustering due to matching and can be thought of as a generalized structural equations model. This approach will allow us to simultaneously assess multiple mediators and will also allow us to consider AHI as a continuous variable. Each model will be fit using likelihood methods and model fit will be checked using appropriate information criteria. After fitting the overall model, we will obtain, for each mediator, an estimate of the indirect effect (e.g. the portion of the overall effect of SDB on PAF mediated through the intermediate variable). A bootstrap resampling technique will be used to obtain a 95% CI for each indirect effect. If the CI does not contain zero, this will indicate statistically significant mediation.

Exploratory Aim 1b. Explore age interactions in the SDB-PAF relationship. Each conditional logistic regression model will include an interaction between age and SDB to investigate if age is a modifier of the effect of SDB on PAF, i.e. whether the odds ratio of PAF for a 1-unit increase in SDB varies by age.

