SA 1. Quantify the extent that SDB and its subtypes are associated with PAF. This aim will be addressed by fitting conditional logistic regression models that condition on the matched pair. We will separately analyze each SDB variable (primary variable: AHI) to obtain an estimate and 95% CI of the odds ratio of PAF for a 1-unit increase in the SDB exposure. Non-linear effects between SDB and the log odds of PAF will be assessed using restricted cubic splines. Knots for the spline will be based on the SDB threshold at which PAF risk increases. Unadjusted and hierarchical adjusted models will be performed using the covariates listed above.

The secondary exposure variables (e.g. hypoxia, OAHI, CAI, AI) will be considered in separate models.

Exploratory Aim 1a. Cardiac structure, autonomic and biochemical variables (Table 2) will explain a proportion of the SDB and PAF relationship. This aim will be addressed by applying Pearl's mediation formula ¹⁰⁸ to the conditional logistical regression model. This approach will allow a causally sound definition of the mediation effect of a given intermediate variable in the relationship between SDB (defined by AHI) and PAF. The approach involves a model for each mediator (e.g. a general linear model for a continuous mediator) and possibly a random effect to account for clustering due to matching and can be thought of as a generalized structural equations model. This approach will allow us to simultaneously assess multiple mediators and will also allow us to consider AHI as a continuous variable. Each model will be fit using likelihood methods and model fit will be checked using appropriate information criteria. After fitting the overall model, we will obtain, for each mediator, an estimate of the indirect effect (e.g. the portion of the overall effect of SDB on PAF mediated through the intermediate variable). A bootstrap resampling technique will be used to obtain a 95% CI for each indirect effect. If the CI does not contain zero, this will indicate statistically significant mediation.

Exploratory Aim 1b. Explore age interactions in the SDB-PAF relationship. Each conditional logistic regression model will include an interaction between age and SDB to investigate if age is a modifier of the effect of SDB on PAF, i.e. whether the odds ratio of PAF for a 1-unit increase in SDB varies by age.

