SA 1. A sample size of 300 will be able to detect an odds ratio of 1.50 with 80% power (and 1.60 with 90% power), assuming a 2-sided alpha level of 0.05, a correlation in AHI between cases and controls of zero and a probability of PAF of 0.20 when AHI is set at its mean value. Note that the odds ratio is interpreted as the odds ratio for PAF for a 1 standard deviation increase in AHI. Alternatively assuming that the probability that $AHI \geq 15$ for patients without PAF is 30% ⁶⁴, a sample size of 150 matched pairs will be able to detect an odds ratio of PAF of 2.13 with 90% power assuming a 2-sided alpha-level of 0.05. Note that this calculation assumes that the correlation for SDB between subjects with and without PAF is 0.20, as suggested by Dupont (1988)¹⁰⁹ when the correlation is unknown. Our prior cross-sectional work demonstrating SDB-AF odds ratio point estimates of 2-4 ^{1,2} supports sufficient power to address this aim.

Exploratory Sub-Aim 1a. To calculate the power to detect mediation, a difference in coefficients approach will be used ¹¹⁰ which involves the fitting of two logistic regression models that model the association between SDB ($AHI \geq 15$) and the log odds of PAF (one with and the other without the potential mediator in the model) to estimate the proportion of exposure effect that is mediated. Assuming a correlation between the adjusted and unadjusted effect estimates of 0.9 and that the probability of PAF in SDB and no SDB is 0.07 and 0.01 respectively (based upon prior data ²), a sample size of 150/group will be able to detect mediation proportions of 0.5 with 84% power assuming a 2-sided 0.05 alpha-level test. Although power may be reduced depending on the observed imbalance in sample sizes for the SDB and no SDB groups, power will be increased due to matching (not taken into account here to be conservative).

SA2. Using a two-sample t-test (2-sided 0.05 alpha-level) to test for a difference in mean variation between the SDB ($AHI \geq 15$) and no SDB groups, a sample size of 150 (75 with SDB and 75 without SDB) will detect mean differences within 0.46 standard deviations with 80% power and 0.53 standard deviations with 90% power.

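### SA1's matched-pair power statement (AHI ≥15, odds ratio 2.13) belongs to no model that SA1 plans to fit; the continuous-AHI power statement does match the planned test

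*Combined protocol and SAP*

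**What the plan says.** The SA 1 power text is the same in sections 9 and 10 and holds two calculations.

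- **Continuous AHI:** "A sample size of 300 will be able to detect an odds ratio of 1.50 with 80% power (and 1.60 with 90% power"). The odds ratio is per 1 SD of AHI. The stated assumptions are zero case-control correlation in AHI and a PAF probability of 0.20 at mean AHI.
- **AHI ≥15, offered as an alternative:** "a sample size of 150 matched pairs will be able to detect an odds ratio of PAF of 2.13 with 90% power". The probability of AHI ≥15 "for patients without PAF is 30" percent, and the calculation "assumes that the correlation for SDB between subjects with and without PAF is 0.20". Alpha is two-sided 0.05.

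The sufficiency argument follows at once: "Our prior cross-sectional work demonstrating SDB-AF odds ratio point estimates of 2-4" are said to support adequate power.

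The SA 1 analysis text uses conditional logistic regression on the matched pair, with each SDB variable analysed separately "to obtain an estimate and 95% CI of the odds ratio of PAF for a 1-unit increase in the SDB exposure". It adds that "Non-linear effects between SDB and the log odds of PAF will be assessed using restricted cubic splines". It names no model with AHI ≥15 versus <15 as the exposure. The primary aims in section 1 promise exposure-response relationships and thresholds, but do not fix a threshold at 15 for SA1.

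**The concern.** A power statement is useful only if it refers to a test that will be run. The 2.13 figure refers to a two-level contrast that SA1 never fits, and the argument from earlier odds ratios of 2-4 is placed directly after it. Two things could go wrong.

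- A null per-unit result could be reported as coming from a study with 90% power for an odds ratio of 2.13, although that power was computed for a different statistic.
- SA1 will produce no odds ratio that can be set beside 2.13, so readers cannot compare the result with the effect the calculation describes.

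**Working it through.** **Inputs from the documents.** Two-sided alpha 0.05. Continuous calculation: 300 participants, P(PAF) = 0.20 at mean AHI, odds ratios 1.50 and 1.60 per SD. AHI ≥15 calculation: 150 pairs, control prevalence 0.30, correlation 0.20, odds ratio 2.13.

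**Step 1: continuous AHI.** N = (1.960 + z)² / [P(1−P)(ln OR)²], with P(1−P) = 0.16.

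- OR 1.50, 80% power: 7.849 / (0.16 × 0.1644) = 298.4, so 299.
- OR 1.60, 90% power: 10.507 / (0.16 × 0.2209) = 297.3, so 298.

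Both agree with 300. Rescaling AHI from SDs to single units changes the coefficient but not the test, so this calculation fits the planned linear term. The formula ignores the matching. Simulated 1:1 conditional logistic fits with 150 pairs give 94% and 98% at zero correlation, and 87% and 95% at correlation 0.20, so the printed figures are not optimistic there.

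**Step 2: AHI ≥15.** Dupont matched-pair formula: solve for the exposure probability in cases that gives a discordant ratio of 2.13 at control prevalence 0.30 and correlation 0.20.

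- Exposed cases 0.4388; case-only exposed 0.2617; control-only exposed 0.1229 (ratio 2.13); discordant proportion 0.3846.
- P = 2.13/3.13 = 0.6805.
- Power = Φ{[(0.6805 − 0.5) × √(150 × 0.3846) − 0.980] / √(0.6805 × 0.3195)} = Φ{(1.371 − 0.980) / 0.4663} = Φ(0.839) = 79.9%.

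Formula variants give 78.9-81.4%. The odds ratio detectable at 80% is 2.132; at 90% it is about 2.38 (2.34-2.42 across variants). Detecting 2.13 at 90% needs about 199 pairs. Power within two points of 90% appears only if a stated input is changed: zero correlation (88.9%), a one-sided test (88.0%) or ignoring the matching (88.7%).

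**Step 3: statements against models.**

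| SA1 power statement | Exposure | Planned SA1 model |
|---|---|---|
| OR 1.50 / 1.60 | AHI per SD | Conditional logistic, AHI per unit (same test) |
| OR 2.13 | AHI ≥15 yes/no | None named |

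**Step 4: size of the mismatch.** The documents give neither an AHI distribution nor the shape of the effect, so these are assumptions. Simulated 1:1 conditional logistic fits, 150 pairs, log-normal AHI capped at 120 with log-SD 0.8-1.4, latent correlation 0.33 (exposure correlation about 0.2), likelihood-ratio tests, discordant ratio at AHI ≥15 set to about 2.13 throughout:

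| Assumed truth | AHI ≥15 model | AHI per unit |
|---|---|---|
| Single step at 15 | 80-83% | 40-45% |
| Linear in log(AHI+1) | 80-82% | 86-91% |
| Linear in AHI (about OR 1.55 per SD) | 77-81% | above 99% |

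Under the step, a 4-knot spline omnibus test has 54-57%. Over a wider set of distributions (log-normal with log-SD 0.4-1.4, gamma, normal), the step gives the per-unit likelihood-ratio test 28-55%, against about 79% for the AHI ≥15 model. With normal AHI, a graded effect and zero correlation, the linear test has 98% and the AHI ≥15 test 90%.

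**The case against.** The strongest reply is that SA1 already has the right calculation. Its first power sentence is for continuous AHI, it reproduces, and the AHI ≥15 figure is offered only as an alternative. That stands. A reader might infer that the planned test has half the power for the effect SA1 was sized on, or that SA1 is underpowered. The documents support neither. SA1 was sized on continuous AHI as well, and an odds ratio across a cut-off does not assert a step at that cut-off. The loss appears under a step and reverses under both graded shapes tried on the same skewed AHI, so skewness alone does not cause it.

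A reader might also infer that the earlier odds ratios of 2-4 were estimated at AHI ≥15 and can be compared only with 2.13. The documents do not give their exposure scale, so that cannot be claimed either.

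Finally, one may say that adding a dichotomised model is a matter of taste and invites choosing the better result. The risk is real but can be contained by naming and ranking the model in advance. What the objection does not remove is a power figure with no test attached, used just before the claim of sufficiency. A step-like effect is also not foreign to the plan, which sets out to find thresholds, though it does not place one at 15.

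**Conclusion.** The mismatch is established from the text alone: the 2.13 statement describes no planned SA1 test. The continuous statement does, and it holds. The practical loss is conditional. Under a single step at AHI 15 with skewed AHI, the per-unit test has about 40-45% power against about 80% for an AHI ≥15 model; under a graded effect the per-unit test is the stronger. The pairing of 2.13 with 90% is wrong on its own inputs, with no assumption beyond the standard matched-pair formula: they give about 80%. This is a point of specification and reporting that should be corrected. It is not evidence that SA1 is too small.

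**What to change.** In sections 9 and 10, SA 1:

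1. Add one pre-specified conditional logistic model with AHI ≥15 versus <15 as the exposure, labelled as a companion to the primary continuous-AHI analysis.
2. Tie the matched-pair power statement to that model only, restated as about 80% power for an odds ratio of 2.13 (or about 2.38 at 90%).
3. Support the continuous analysis with its per-SD figures only.
4. State the exposure scale of the earlier odds ratios of 2-4 before using them to support either calculation.

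The cost is SAP wording and one more model on data already collected. The downside is one more named contrast, which must stay secondary so that the more favourable result is not chosen afterwards.

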11. POTENTIAL RISKS

There are no serious risks to study participation. The study procedures do not place subjects at greater risk of harm or discomfort than those encountered in routine medical care. Intravenous catheter placement and venous sampling is associated with temporary pain at the time of needle insertion, may result in bruising at the needle insertion site and occasional fainting. Blood pressure measurements may cause some discomfort associated with cuff inflation. Sleep monitoring may disturb sleep. The anthropometry uses a measuring tape and metal calipers, and the pinch from the measuring tape and calipers may cause some mild discomfort related to tugging on your skin. This disappears almost immediately after the measurement is made. The attachment of the sensors during sleep monitoring, the MultiSense™ sensor and ECG monitoring may cause skin irritation. However, the latter is usually minor and temporary. The participant may feel some pressure at the site of the probe that is used to perform echocardiography. If you require an echocardiogram with a contrast dye, you will receive an intravenous (IV) administered contrast dye that contains microscopic bubbles during your echocardiogram. This type of contrast dye may, in rare cases, cause severe and potentially life-threatening allergic reactions, including a drop in blood pressure, difficulty breathing, fainting, and internal organ failure. This agent may also cause temporary minor back pain, a headache, and/or itchy skin all of which usually goes away within 30 minutes. You will be closely monitored for about 30 minutes after your echocardiogram is complete by a doctor. There are no significant risks associated with 6-minute walk testing.

Accidental breaching of confidentiality is a recognized risk to all studies that collect patient-level data; however, as described below there are multiple levels of safety measures that are taken to avoid this.

CPAP is the most commonly prescribed treatment for SDB. The use of CPAP can be associated with a number of minor side effects, including nasal congestion, runny nose, dry nose or mouth, eye irritation from mask leaks, skin irritation from the mask, or discomfort from the mask or air pressure. PAP therapy may rarely cause nose bleeds and can cause worsening of a sinus condition or abdominal bloating. The potential for skin and eye irritation is minimized by proper mask fit and use of a humidifier and application of appropriate pressure levels.

The risks of the 7T MRI sub-study are the same as the risks of a routine MRI of the brain. MRI has no known long term risks. There are no known biological risks associated with MR imaging. An MRI may cause possible anxiety for people due to the confined space of the testing area resulting in feelings of claustrophobia and the loud banging made by the machine. Protective headphones that minimize the noise inside the MRI and allow the technologists to talk to you directly to the participant will be used.. Some people feel discomfort associated with lying still within the MR scanner. The use of a bite block may assist in keeping still. There may be local pain and bruising during the placement of the IV. Patients with severe kidney disease are at risk for developing a serious systemic fibrosing disease, NSF. Anyone with severe kidney disease will not be

placed in this study.

If a bite bar is used, there is a possibility of some discomfort from this device including fatigue of the jaw muscles or muscle tiredness of the neck. In addition, a small percentage of people have a very sensitive gag reflex, which may prevent the use of a bite bar.

Since the MRI is a powerful magnet, participants cannot be scanned if they have certain metal devices in their body such as a cochlear (ear) implant, brain aneurysm clip, implanted stimulator device, or cardiac pacemaker. If any devices or implants or if they have a history of metal in their eye or body, the MR technologist will be notified. There is also a risk of injury if metal is brought into the imaging room, which may be pulled into the magnet. No magnetic objects (pocket knives, key chains, necklaces, earrings) from clothes and body will be allowed in the scanner area to prevent any injuries. A Safety zone is established around the MR scanner to prevent objects containing iron from coming into contact with the scanner.

Repeated evaluations of mood and mental status may be slightly frustrating or produce fatigue and boredom. Rest breaks will be provided during cognitive testing, and the study staff members are trained to offer assistance and to discontinue testing if necessary.

Protection Against Risks.

A. RECRUITMENT AND INFORMED CONSENT

Trained research personnel who have completed necessary certification for human subject research will screen Electrophysiology (EP) Clinic referrals for cases (those with PAF), Cardiology/Internal Medicine clinics for controls (those without AF) and supplementary recruitment from the Echocardiography Database for controls (those without AF). Participants will be screened when presenting for a routine EP clinic visit (or Cardiology/Internal Medicine visit for controls), after the caring physician has ascertained that the patient may be interested in learning more about the study and meeting study staff. When meeting with the research staff (at the clinic visit or another scheduled time), full written informed consent will be obtained. Alternatively, the charts of potentially eligible cases with PAF will be marked to inform the EP physician of eligibility. The physician will be asked to briefly discuss the study with the patient and assess interest. Patients who express interest will be contacted by study staff to further review the study protocol and if interested, a face to face meeting will be arranged to fully review the protocol and obtain informed consent. Consent forms will explain in a lay persons' terminology the nature of all procedures. It will be stressed that participation is voluntary. The research assistant and PI will be available to answer questions. The investigator will also be available to answer questions about the study then or at other times. Participants are also informed that at any time that can request that any stored blood be discarded and not used for research purposes. All activities will be compliant with local IRB and HIPPA guidelines, such as obtaining physician permission to initiate

contact, destroying all pre-screening forms, and obtaining verbal permission, as appropriate for phone interviews. At the beginning of the study, and then periodically, any IRB, HIPAA or privacy requirements that may be in effect at that time also will be checked to assure that plans are compliant with current rules.

Although the clinics will be the primary source of recruitment, controls we will also assess eligibility of individuals from the UHCMC/CCF Echocardiography Database (>10000 ECHOs/year). [name] will identify patients who meet matching criteria (left ventricular function, age, sex, race) based upon the cases who have been enrolled in the study. Referring physicians will be notified through emails or phone calls when eligible patients are identified. A letter signed by [name], the PI and the physician who referred the patient for the ECHO will then be sent to these patients describing the research study and providing study contact information. A time will be arranged for the patient to meet the research staff in a face to face meeting fully review the protocol and obtain informed consent.

B. PROTECTION AGAINST RISKS

All participant information will be kept strictly confidential and used for research purposes only. Records will be identified by a subject ID number rather than the subjects' name, and all will be secured in locked files in secured rooms. Computers are located in restricted access research suites; computer information is protected by use of passwords and a firewall. Computer files do not permit linking individual data with medical or other data collected for research purposes. The list of names and identification numbers will be stored separately from other data in locked files to which project staff only will have access. Informed consents explicitly state that information on non-paternity is never revealed. All presentations and publications will only utilize aggregate data.

Data transmission between the Electrophysiology Core and Echocardiography Laboratory and the Administrative Center-CC will be accomplished through a secure, password protected website using a Virtual Private Network (VPN), an established method for secure transfer. Implementation of this method will prevent unauthorized viewing of participant information during data transmission. The Administrative Center-CC and Cores will not receive any information allowing participant identification. Participant data received by the Administrative Center-CC will be identified only by the participant ID.

Risks will be minimized by using hypoallergenic materials, appropriate fitting of nasal CPAP masks and use of a humidifier with the PAP devices. If nasal symptoms are experienced, a study physician will contact the participant and determine if an over-the-counter or prescription decongestant is needed. Visits will be scheduled during a time when the individual is stable and free of acute illnesses. Staff will be trained and certified to perform phlebotomy and other research procedures.

Abnormal findings requiring urgent evaluation may also be identified at the time of the DCRU/CRU visits. All such findings will be labeled as adverse events (AEs) or serious adverse events (SAEs) as appropriate. A blood pressure finding of systolic greater than

Elucidation of the Influence of Sleep Apnea on Risk of Atrial Fibrillation PI- [name] and [name]

180 or diastolic greater than 120 will result in evaluation of the patient in the DCRU/CRU to assess for evidence of end organ dysfunction. Such a finding will lead to immediate transfer to the emergency room for acute blood pressure treatment. Asymptomatic hypertension without evidence of end organ dysfunction will result in contact being made with the patient's primary care physician to notify them of the finding or if the patient does not have a primary care physician, referral to a clinic to provide antihypertensive treatment. Similarly, participants with an increased heart rate (i.e. >120bpm) will undergo medical evaluation by a physician (PI or physician designate) in the CRU. If the participant is deemed unstable, then the participant will be sent to the emergency department.

It is also possible the concerning arrhythmias or concerning symptoms may arise during the 7-21 day continuous ECG monitoring. Cardiology Diagnostic Services has certified ECG technicians who are monitoring the heart rhythms in real-time and also are the contact source for the participants to call 24-7 if there are symptoms during the monitoring. If the technician identified a serious arrhythmia (e.g. high degree atrioventricular block, ventricular tachycardia, atrial fibrillation with rapid rate (>120bpm)) or concerning symptoms, then the PI will be contacted directly and the patient will sent to the emergency room for evaluation.

Intravenous catheter and blood sample collection may cause a small bruise that is temporarily uncomfortable, but will disappear in several days. A topical anesthetic will be used to minimize discomfort when necessary. To minimize the possibility of fainting, the intravenous catheter and blood sample collection will take place while the participant is sitting.

A medical release will be given to the participants to sign to authorize release of their health information to their physician if there is any urgent health information that requires immediate attention. Letters outlining results of the sleep study will be sent to the participant and with the permission of the participant will also be sent to the primary care or caring physician to arrange for appropriate treatment and follow-up of sleep disordered breathing.

Data Safeguarding Plan: Data security is addressed at many levels. The database administrator will be responsible for providing and documenting appropriate user access to the study database, preventing such data security problems as: unauthorized internal access to data, external access to data, and malicious intent to destroy data and systems. Data audit software and systems will be used that document data modification, user access associated with modification, data associated with modification, and values prior to modification.

The database administrator will also be responsible for optimizing database performance, reliability and back-up of data. Data transmission amongst the Administrative Center-CCI and the Cores and University of Vermont will be accomplished through a secure, password protected website using a Virtual Private Network (VPN), an established method for secure data transfer, and use of encryption.

Study investigators and staff will be provided with user accounts and passwords. All presentations and publications will only utilize aggregate data. All UHCMC and CCI staff will be trained and certified in the ethical conduct of research.

De-identified study data will be hosted on a server in a private network only accessible through VPN. The computer server will be hardened according to the data security guideline and check-list by the UHCMC Data Security division, with the study database environment reviewed by the UHCMC Data Security team before implementation.

Additional security measurements such as 128-bit encryption for SSL, auditing trail, and data encryption at rest will be implemented as appropriate.

SOURCES OF MATERIALS

The research data will be collected strictly for research and include polysomnography, echocardiography, electrocardiography (from polysomnography and 7-21 day ECG monitoring), anthropometry, blood pressure and blood or urine assayed for markers of inflammation and oxidative stress. Questionnaires addressing medical conditions, medications, sleep habits and symptoms will be administered. Participants will be asked to provide permission to obtain health records for medical encounters in order to adjudicate adverse events if needed. Other data that will be reviewed to ascertain eligibility will be from the echocardiography database and medical records. In addition, for those placed on CPAP, CPAP compliance and residual apnea hypopnea index using CPAP will be ascertained using data electronically stored on the CPAP units participants will be using.

Linkages to subjects and access to research data: All research data will be collected on standardized research forms with de-identified ID numbers, but without personal identifiers. Any data collected from medical records will be entered onto case report forms with only visit ID numbers, excluding personal identifiers. Only study personnel will have access to research data which is kept in either locked cabinets or password computers in locked buildings. All personal data will be stored separately from de-identified research data. The primary data files are stored in locked cabinets in secured rooms in this research facility. Bloods will be stored using de-identified bar codes at the Core Laboratory at Case until shipped to University of Vermont. All data transmitted to the Administrative Center-CCI will include no personal identification data. Data received at Administrative Center-CCI will be stored in a dedicated MySQL system in a server within a private network. Access to such data will be through VPN and a dually-authenticated client computer. Access to the query, exploration and exchange interface of the customized Physio-MIMI system will be permitted only to authorized team members using the resident secure, Role-Based Access Control mechanism.

12. POTENTIAL BENEFITS TO THE SUBJECTS AND OTHERS AND IMPORTANCE OF THE KNOWLEDGE TO BE GAINED

There are a number of potential benefits to participants. All participants that undergo sleep apnea screening will be provided information on the results of their sleep studies which may be useful in further health management. Participants started on CPAP may further experience direct benefit related to the direct treatment of underlying sleep apnea.

At completion of the study, participants will receive summary results of their sleep patterns from polysomnography, CPAP usage data plus review of their symptoms in the context of normative data (e.g., Epworth sleepiness score) as well as blood pressure findings. If approved by the subject, these results will also be sent to the subject's physician. Participants will also receive a monetary compensation of \$75 for each overnight visit to the DCRU/CRU for their time. To receive payment the participant must agree to complete a W-9 form which requires them to provide an address and social security number to the accounting department. This payment may be considered taxable income by the IRS. The participant will be issued a 1099-Misc form only if payment exceeds \$600 from all studies in which they are participating, in a fiscal year. Parking costs will be covered and participant will receive dinner and breakfast during the DCRU/CRU stay. We also believe that the gains in understanding of the relationship between SDB and an important outcome, atrial fibrillation, will outweigh any potential risk to the participants. Since the risks of participation for individual subjects are extremely low, and the benefits to society are potentially large, the risk-benefit ratio is more than acceptable. Participants who choose not to participate in this study may seek evaluation and treatment for possible SDB from their physician.

SDB is very common, and may have serious adverse health consequences such as increased risk of clinically significant arrhythmias such as AF and associated increase in morbidity and mortality. The proposed study will further explore linkages between SDB and PAF, as well as help to elucidate the pathophysiology of these associations. Given that SDB is treatable, improved understanding of these interrelationships of SDB and AF could have very significant clinical impact.

Research Injury Language:

